13.1.2.4 Decision Rule

Previous studies in relapsed or refractory ALL have shown a CR rate ranging from 20 to 47% (61, 62). Responses can vary by factors such as first or second relapse and age. Due to the heterogeneity of this disease, a response rate of 10% with MLN0128 (TAK-228) would not be of interest. The largest success proportion where the proposed treatment regimen would be considered ineffective in this population is 10%, and the

smallest success proportion that would warrant subsequent studies with the proposed regimen in this patient population is 30%. The following one-stage design with an interim analysis uses 26 evaluable patients to test the null hypothesis that the true success proportion in a given patient population is at most 10%.

13.1.2.5 Interim Analysis

Enter 11 evaluable patients into the study. If 1 or fewer successes are observed in the first 11 evaluable patients, we will consider this regimen ineffective in this patient population and terminate this study. Otherwise, if the number of successes is at least 2, we will continue accrual.

13.1.2.6 Final Decision Rule

Enter 26 evaluable patients into the study. If 4 or fewer successes are observed in the first 26 evaluable patients, we will consider this regimen ineffective in this patient population. If 5 or more successes are observed in the first 26 evaluable patients, we may recommend further testing of this regimen in subsequent studies in this population.

13.1.2.7 Over Accrual

If more than the target number of patients are accrued at the safe dose, the additional patients will not be used to evaluate the stopping rule or used in any decision making process; however, they will be included in final endpoint estimates and confidence intervals.

NOTE: We will not suspend accrual at the interim analysis to allow the first 11 patients to become evaluable, unless undue toxicity is observed. Given the limited overall sample size and the inclusion of an adverse events stopping rule, we feel it is ethical to not halt accrual for the interim analysis. However, if accrual is extremely rapid, we may temporarily suspend accrual in order to obtain safety data on these patients before re-opening accrual to further patients.

13.1.3 Power and Significance Level

Assuming that the number of successes is binomially distributed, the significance level is .09, i.e. there is a 9% chance of finding the drug to be effective when it truly is not. The probability of declaring that this regimen warrants further study (i.e. statistical power) and the probability of stopping at the interim analysis under various success proportions can be tabulated as a function of the true success proportion as shown in the following table.

If the true success proportion is...	0.10	0.15	0.20	0.25	0.30
Then the probability of declaring that the regimen warrants further study is...	0.09	0.28	0.52	0.72	0.85
and the probability of stopping at the interim analysis is ...	0.70	0.49	0.32	0.20	0.11

13.1.4 Other Considerations

Adverse events, quality/duration of response, and patterns of treatment failure observed in this study, as well as scientific discoveries or changes in standard care will be taken into account in any decision to terminate the study.

13.2 Sample Size/Accrual Rate

13.2.1 Sample Size

The one-stage design with an interim analysis to be utilized is fully described above. A maximum of 26 evaluable patients will be accrued onto this phase II study unless undue toxicity is encountered. If there is undue toxicity in the initial safety cohort (see section 13.5), an additional 6 patients will be accrued. Further, we anticipate accruing an additional 3 patients to account for ineligibility, cancellation, major treatment violation, or other reasons. Therefore, the maximum projected accrual is 35 patients.

13.2.2 Accrual Rate and Study Duration

The anticipated accrual rate is 1 evaluable patient per month. Therefore, the accrual period for this study is expected to be approximately 3 years. The final analysis can begin approximately 3.5 years after the trial begins, i.e. as soon as the last patient has been on treatment for 6 months.

13.2.3 Inclusion of Women and Minorities

13.2.3.1 This study will be available to all eligible patients, regardless of race, gender, or ethnic origin.

13.2.3.2 There is no information currently available regarding differential effects of this regimen in subsets defined by race, gender, or ethnicity, and there is no reason to expect such differences to exist. Therefore, although the planned analysis will, as always, look for differences in treatment effect based on racial and gender groupings, the sample size is not increased in order to provide additional power for subset analyses.

13.2.1.3 The geographical region served by Mayo Clinic has a population that includes approximately 7% minorities. Based on prior Mayo phase 2 studies involving similar disease sites, we expect about 7% of patients will be classified as minorities by race and about

55% of patients will be women. Expected sizes of racial by gender subsets are shown in the following table:

DOMESTIC PLANNED ENROLLMENT REPORT						
Racial Categories	Ethnic Categories				Total	
	Not Hispanic or Latino		Hispanic or Latino			
	Female	Male	Female	Male		
American Indian/ Alaska Native	0	0	0	0	0	
Asian	0	0	0	0	0	
Native Hawaiian or Other Pacific Islander	0	0	0	0	0	
Black or African American	1	1	0	0	2	
White	18	13	1	1	33	
More Than One Race	0	0	0	0	0	
Total	19	14	1	1	35	

13.3 Stratification Factors

None.

13.4 Analysis of Secondary/Tertiary Endpoints

- 13.4.1 The overall response rate will be estimated by the total number of complete or partial responses (CR, CRi, PR, or MLFS) divided by the total number of evaluable patients. All evaluable patients will be used for this analysis. Exact binomial 95% confidence intervals for the true overall response rate will be calculated.
- 13.4.2 Duration of complete response (CR/CRi) is defined for all evaluable patients who have achieved a complete response as the time from the date at which the patient's objective status is first noted to be a CR to the earliest date progression is documented. The distribution of duration of complete response will be estimated using the method of Kaplan-Meier.
- 13.4.3 The frequency of proceeding to allogeneic SCT after achieving response (CR, CRi, PR, or MLFS) to MLN0128 (TAK-228) will be estimated by the number of patients who proceed to allogeneic SCT after achieving response divided by the total number of

evaluable patients who achieved a response. All evaluable patients who achieved a response will be used for this analysis. Exact binomial 95% confidence intervals for the true overall response rate will be calculated.

13.4.4 Overall survival time is defined as the time from registration to death due to any cause. The distribution of survival time will be estimated using the method of Kaplan-Meier.

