11.1.2 Response Criteria

11.1.2.1 Evaluation

Complete hematologic response (CR)

Less than 5% blasts in a non-hypocellular marrow with a granulocyte count of $1 \times 10^9/L$ (or above), and a platelet count of $100 \times 10^9/L$ (or higher) and absence of peripheral blood blasts with complete resolution of any extra medullary disease. The patient is in sustained CR if they have previously achieved a CR and continue to meet the CR criteria (at least 28 days).

CR incomplete (CRi)
is called if patient meets all CR criteria except for residual neutropenia ($ANC < 1 \times 10^9/L$) or thrombocytopenia (platelets $< 100 \times 10^9/L$)

Partial Response (PR):
The presence of trilineage hematopoiesis in the bone marrow with recovery of ANC and platelet count to above levels, but with 5-25% bone marrow blasts and $\geq 50\%$ decrease in bone marrow blast percentage from baseline.

Morphologic leukemia-free state (MLFS)
If bone marrow blasts $< 5\%$, absence of Auer rods blasts, absence of extra medullary disease without hematological recovery.

No response (NR):
Failure to achieve CR/CRi/PR/MLFS after 2 cycles of MLN0128 (TAK-228).

Disease Progression:
At least a 25% increase in the absolute number of circulating blasts in peripheral blood, or at least 25% increase in bone marrow blasts, or development of extramedullary disease.

Relapse
Disease recurrence after achieving CR. Disease recurrence is defined by blast $\geq 5\%$ in the bone marrow, or recurrence of peripheral blood $> 5\%$ or extramedullary involvement.

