11.1.3 Duration of Response

Duration of response is the duration of CR or CRi is measured from the time measurement criteria are first met for CR until the first date that recurrence is objectively documented.

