13.1.2.1 Definition of Primary Endpoint

The primary endpoint of this trial is complete response rate. A complete response is defined to be a CR or CRi noted as the objective status at any time during treatment. Response will be evaluated using all cycles of treatment. All patients meeting the eligibility criteria who have signed a consent form and have begun treatment will be evaluable for response.

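### CR/CRi duration ends at progression in 13.4.2 but at recurrence in 11.1.3, and 11.1.2.1 defines these as different events

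*Combined protocol and SAP*

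**What the plan says.** Two sections of the combined protocol and SAP define the duration of complete response.

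- **Section 13.4.2** takes it from the date the patient's status is "first noted to be a CR to the earliest date progression is documented", estimated by Kaplan-Meier.
- **Section 11.1.3** takes it from the time the CR criteria are first met "until the first date that recurrence is objectively documented".

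Section 11.1.2.1 then gives progression and relapse separate definitions.

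- **Progression** has three alternatives: at least a 25% "increase in the absolute number of circulating blasts in peripheral blood", "or at least 25% increase in bone marrow blasts", or new extramedullary disease. No reference value is given.
- **Relapse** is "Disease recurrence after achieving CR". It requires marrow blasts of 5% or more, a peripheral-blood criterion above 5%, or extramedullary involvement.
- **CR** requires fewer than 5% marrow blasts and "absence of peripheral blood blasts with complete resolution of any extra medullary disease". CRi differs only in allowing residual neutropenia or thrombocytopenia.

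On who counts as a complete responder, Section 13.1.2.1 states: "A complete response is defined to be a CR or CRi noted as the objective status at any time during treatment". Both duration sections nevertheless start the clock at CR alone.

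**The concern.** An analyst programming objective 1.2.2 from Section 13.4.2 would look up progression in Section 11.1.2.1. An analyst working from Section 11.1.3 would look up relapse. These are different tests. One is a proportional or additive rise from an unstated starting point; the other is a fixed level. The same patient could therefore leave remission on two different dates, or meet one definition and not the other. With few responders expected, the reported duration could depend on which section was followed, and the choice might be made after the responders' outcomes are known.

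The start date has a smaller version of the same problem. Read literally, a patient who reaches CRi but never CR has no start date, and one who moves from CRi to CR starts late, although both are complete responders under Section 13.1.2.1.

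**Working it through.** The plan states no precision, power or expected value for response duration, so there is no figure to reproduce. The check compares the two definitions as they apply to a patient already in CR.

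**1. Circulating blasts.** CR requires none. If the reference is the remission count, the required count is 1.25 × 0 = 0, so a 25% rise has no meaning. A pretreatment reference would be usable for patients with circulating blasts at entry, but the text does not state one. Because the criterion is written for an absolute number of blasts, relative versus percentage points is not in doubt here; only the reference is missing.

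**2. Marrow blasts.** Here both the reference and the scale are unstated. Inputs: relapse at 5%; remission marrow below 5% (CR definition); pretreatment marrow at least 10% (Section 3.1.2).

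| Reading of the 25% rise | Calculation | Progression threshold | Against relapse at 5% |
|---|---|---|---|
| Relative to a remission value of 2% | 1.25 × 2 | 2.5% | Lower |
| Relative to a remission value of 3% | 1.25 × 3 | 3.75% | Lower |
| Relative to a remission value of 4% | 1.25 × 4 | 5.0% | Equal |
| Relative to a pretreatment value of 10% | 1.25 × 10 | 12.5% | Higher |
| Relative to a pretreatment value of 50% | 1.25 × 50 | 62.5% | Higher |
| Percentage points above a remission value of 0% to 4% | 0 + 25 to 4 + 25 | 25% to 29% | Higher |

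The remission values are illustrations within the CR limit. For a pretreatment marrow above 80%, the relative reading asks for more than 1.25 × 80 = 100% blasts and can never be met.

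**3. Extramedullary disease.** New extramedullary disease ends remission under both definitions. This is the only shared criterion.

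**4. Number of patients involved.** Among the 26 evaluable patients in the design, expected complete responders are 26 × 0.10 = 2.6 at the null rate and 26 × 0.30 = 7.8 at the target rate. These figures show scale and are not bounds. Stopping at the interim would lower them. Over-accrued patients, who enter the final estimates under Section 13.1.2.7, or the 6 extra patients allowed in Section 13.2.1, could raise them.

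**The case against.** The best defence is that progression in Section 13.4.2 is simply a general word for loss of response. Sections 5 and 5.3 use it that way when they say when a responder stops treatment. Section 11.1.2.1 supplies a definition of recurrence made for patients in remission, and a patient going from 2% to 2.5% marrow blasts still meets the CR marrow criterion, so nobody would sensibly call that the end of remission. In addition, the only reference the response criteria name anywhere is baseline (in the PR definition), and that reading gives only later dates.

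Much of this stands. Loose wording is quite possibly the explanation, and the early date is the least plausible reading. But progression is a defined term in this protocol, and the baseline reading also disagrees with relapse. If the intended event is relapse, Section 13.4.2 names the wrong one.

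A reader might infer three stronger points, which the documents do not support:

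- **That the missing rule for death or transplant in remission is itself an error.** Section 13.4.2 names one event under Kaplan-Meier, while Section 13.4.4 names death for overall survival. On an ordinary reading, responders without the named event are censored. An explicit sentence would help, but its absence is a missing detail and does not carry this point. The rule in Section 13.7.2 that treats early deaths as failures concerns the response rate and does not settle the matter.
- **That the duration estimate is distorted by a known amount.** One responder's share of a small group does not measure how far the curve moves when an event is redated. Both thresholds could be crossed at the same marrow examination. The calendar grid is not legible in the text available, so the assessment interval cannot be used.
- **That the trial's conclusion is at risk.** The primary endpoint is CR or CRi at any time during treatment and does not use duration.

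**Conclusion.** The inconsistency is real. Sections 13.4.2 and 11.1.3 end the same endpoint at two separately defined events. Taken literally, the event in Section 13.4.2 is undefined for circulating blasts when referenced to remission, and for marrow it can fall before or after relapse depending on an unstated reference and scale.

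The scope is narrow: one descriptive secondary endpoint with few expected responders. The primary endpoint, the numerical interim rule and the power are unaffected. Section 13.1.4 lists duration of response among matters that may bear on terminating the study, which is a further reason for a single definition, but no decision boundary uses it.

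The conclusion rests on the wording of the three sections, the CR blast limits and the 10% eligibility floor. It does not assume that any patient's date would in fact change, and no numerical effect on the Kaplan-Meier estimate can be derived from the documents.

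**What to change.** In Section 13.4.2, replace progression with relapse (recurrence) as defined in Section 11.1.2.1, so that it matches Section 11.1.3. In the same edit, start the clock in both sections at first CR or CRi, and word the Relapse definition to apply after CR or CRi.

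Two clarifications are optional and do not carry the point:

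- Add one sentence saying how death and transplant in remission enter the analysis.
- Complete the relapse criterion printed as "or recurrence of peripheral blood" above 5%, presumably meaning blasts, since Section 13.4.2 would then depend on it.

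The cost is a few words in Sections 13.4.2, 11.1.3 and 11.1.2.1. Sample size, primary analysis and decision rules stay as they are. The edit is best made before responders' outcomes are known, so that the choice of event cannot be influenced by the data.

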13.4.5 Adverse Events

All eligible patients that have initiated treatment will be considered evaluable for assessing adverse event rate(s). The maximum grade for each type of adverse event will be recorded for each patient, and frequency tables will be reviewed to determine patterns. Additionally, the relationship of the adverse event(s) to the study treatment will be taken into consideration.

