13.5 Safety Analysis

13.5.1 A safety analysis will be performed after the first 6 patients have been accrued to the study on dose 0 (3 mg, orally days 1-21). If 2 or more of the first 6 patients experience a dose-limiting toxicity (DLT) as defined below, then 6 patients will be enrolled on dose -1 (2 mg, orally days 1-21). If 2 or more of the second 6 patients experience DLT, then the study will be terminated.

13.5.2 Toxicity will be measured per NCI-CTCAE version 4. DLT is defined as an adverse event possibly, probably, or definitely related to study treatment that meets one of the following:

- Any grade 4 drug-related non-hematological toxicity
- Any grade 3 drug-related non-hematological toxicity that does not resolve to < grade 3 within 3 days, with the following exceptions:
 - Grade 3 Bilirubin, AST, ALT, Alkaline phosphatase will be considered DLT only if it does not recover to <grade 3 within 7 days
- Myelosuppression: hypoplasia (bone marrow cellularity <10%) >50 days

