13.6.1 Adverse Event Stopping Rule

The stopping rules specified below are based on the knowledge available at study development. We note that the Adverse Event Stopping Rule may be adjusted in the event of either (1) the study re-opening to accrual or (2) at any time during the conduct of the trial and in consideration of newly acquired information regarding the adverse event profile of the treatment(s) under investigation. The study team may choose to suspend accrual because of unexpected adverse event profiles that have not crossed the specified rule below.

Accrual will be temporarily suspended to this study if at any time we observe events considered at least possibly related to study treatment (i.e. an adverse event with attribute specified as “possible”, “probable”, or “definite”) that satisfy any of the following:

- If 3 or more out of the first 12 treated patients experience grade 4 non-hematological toxicities at least possibly related to treatment excluding fatigue, fever, infection, and lab abnormalities (hyper- or hypokalemia, hypocalcemia, hyperuricemia, hypophosphatemia) that resolve within 7 days without jeopardizing patient safety.
- If after the first 12 patients have been treated, 25% of patients experience grade 4 non-hematologic toxicities at least possibly related to treatment excluding fatigue, fever, infection, and lab abnormalities (hyper- or hypokalemia, hypocalcemia, hyperuricemia, hypophosphatemia) that resolve within 7 days without jeopardizing patient safety.

We note that we will review grade 4 and 5 adverse events deemed “unrelated” or “unlikely to be related”, to verify their attribution and to monitor the emergence of a previously unrecognized treatment-related adverse event.

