13.7 Reporting and Exclusions

13.7.1 Evaluation of Toxicity

All patients will be evaluable for toxicity from the time of their first treatment with MLN0128 (TAK-228).

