13.7.2 Evaluation of Response

All patients included in the study must be assessed for response to treatment, even if there are major protocol treatment deviations or if they are ineligible. Each patient will be assigned one of the following categories: 1) complete response, 2) partial response, 3) stable disease, 4) progressive disease, 5) early death from malignant disease, 6) early death from toxicity, 7) early death because of other cause, or 9) unknown (not assessable, insufficient data). [Note: By arbitrary convention, category 9 usually designates the “unknown” status of any type of data in a clinical database.]

All of the patients who met the eligibility criteria (with the possible exception of those who received no study medication) should be included in the main analysis of the response rate. Patients in response categories 4-9 should be considered to have a treatment failure (disease progression). Thus, an incorrect treatment schedule or drug administration does not result in exclusion from the analysis of the response rate. Precise definitions for categories 4-9 will be protocol specific.

All conclusions should be based on all eligible patients. Sub analyses may then be performed on the basis of a subset of patients, excluding those for whom major protocol deviations have been identified (e.g., early death due to other reasons, early discontinuation of treatment, major protocol violations, etc.). However, these sub analyses may not serve as the basis for drawing conclusions concerning treatment efficacy, and the reasons for excluding patients from the analysis should be clearly reported. The 95% confidence intervals should also be provided.

REFERENCES

1. Cancer Facts and Figures 2012. American Cancer Society. 2012.
4. Litzow MR. Novel therapeutic approaches for acute lymphoblastic leukemia. *Hematology/Oncology clinics of North America*. 2011;25:1303-17.

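### Section 13.4.5 bases adverse-event rates on eligible treated patients only, while 11.1.1 and 13.7.1 count every treated patient

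*Combined protocol and SAP*

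**What the plan says.** Section 13.4.5, which specifies the adverse-event rates and the maximum-grade frequency tables, sets two conditions, eligibility and having started treatment: "All eligible patients that have initiated treatment will be considered evaluable for assessing adverse event rate(s").

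Section 13.7.1, in the same statistical chapter under Reporting and Exclusions, sets only one: "All patients will be evaluable for toxicity from the time of their first treatment with MLN0128 (TAK-228"). Section 11.1.1 says the same in identical words.

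The safety decision rules carry no eligibility condition either. The stopping rule in 13.6.1 reads "If 3 or more out of the first 12 treated patients experience grade 4 non-hematological toxicities at least possibly related to treatment", and the DLT review in 13.5.1 reads "A safety analysis will be performed after the first 6 patients have been accrued to the study on dose 0".

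The plan expects that some patients may prove ineligible. Section 13.2.1 says "we anticipate accruing an additional 3 patients to account for ineligibility, cancellation, major treatment violation, or other reasons". Section 13.7.2 requires a response assessment for ineligible patients as well.

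**The concern.** A patient who takes the drug and is later found ineligible is in the toxicity population under 11.1.1 and 13.7.1, and out of it under 13.4.5. The restrictive wording sits in the section an analyst would open to program the adverse-event tables.

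Three things are at stake.

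- **Completeness.** The published rates could omit people who were exposed to the drug.
- **Consistency.** A grade 4 event in such a patient could help trigger suspension under 13.6.1 and then be missing from the final table.
- **Timing.** Eligibility can be judged after dosing, when toxicity is already known. The criteria leave room for such disputes. Section 3.1.3 makes exceptions to the 4-week washout only for hydroxyurea and glucocorticoids, while 3.2.1 also allows tyrosine kinase inhibitors up to 24 hours before therapy. Section 3.1.8 refers to a listed limit on prior induction regimens, but none is listed.

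The exclusion may also not be neutral. Several entry limits (fasting glucose and HbA1c, creatinine, QTc) concern the same organ systems as risks listed for the drug in 7.1.1: hyperglycemia, increased creatinine and QT prolongation.

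**Working it through.** **Populations side by side**

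| Section | Use | Who counts | Eligibility required? |
|---|---|---|---|
| 11.1.1 | Toxicity evaluability | All, from first dose | No |
| 13.7.1 | Toxicity evaluability | All, from first dose | No |
| 13.5.1 | DLT review | First 6 accrued at dose 0 | No |
| 13.6.1 | Stopping rule | Treated patients | No |
| 13.4.5 | Adverse-event rates and tables | Started treatment | **Yes** |

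The eligibility condition in 13.4.5 resembles the response population in 13.1.1 and 13.1.2.1 (eligible, consented, treatment begun). Section 13.7.2 also rests its conclusions on eligible patients, but under the heading Evaluation of Response. Neither gives a reason for removing exposed patients from safety tables.

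**Plan's own figure.** From 13.2.1: "A maximum of 26 evaluable patients will be accrued onto this phase II study unless undue toxicity is encountered"; after undue toxicity in the first cohort, "an additional 6 patients will be accrued"; plus the allowance of 3. That gives 26 + 6 + 3 = 35, which matches the stated maximum. Without the extra cohort it is 26 + 3 = 29.

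**How many patients.** Let m be the number treated but ineligible. The documents do not give m. I assume m = 1 to 3, with 3 being the entire allowance. The largest share is then 3/29 = 10.3%, or 3/35 = 8.6% with the extra cohort.

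**Effect on a rate, fixed eligible-only table.** Suppose 4 of 32 eligible patients have an event: 4/32 = 12.5%. The all-treated rate runs from 4/(32 + m), if no ineligible patient had the event, to (4 + m)/(32 + m), if all did.

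| m | None had it | All had it |
|---|---|---|
| 1 | 4/33 = 12.1% | 5/33 = 15.2% |
| 2 | 4/34 = 11.8% | 6/34 = 17.6% |
| 3 | 4/35 = 11.4% | 7/35 = 20.0% |

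**Effect on a rate, fixed all-treated total.** Suppose 5 of 29 treated patients have an event: 5/29 = 17.2%. Restricting to eligible patients gives 4/28 = 14.3% to 5/28 = 17.9% for m = 1, and 2/26 = 7.7% to 5/26 = 19.2% for m = 3.

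**Chance of omitting at least one event.** This is 1 − (1 − q)^m for a true event rate q. With q assumed between 10% and 25%, it runs from 10% (m = 1, q = 10%) to 1 − 0.75³ = 58% (m = 3, q = 25%).

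**Mismatch with the stopping rule.** The trigger of 3 in 12 treated is 25%. If one of those three patients proved ineligible, the table under 13.4.5 would show 2/11 = 18.2% for the same 12 patients.

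The adverse-event population does not enter the response decision rule, so sample size, significance level and power are unchanged.

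**The case against.** The best defence is that nothing is lost where it matters most. Section 7.4 requires all adverse events in routine submissions, and 7.3.3 requires serious events to be reported whether or not related. The DLT review and stopping rule carry no eligibility condition, and 13.6 has the DSMB review safety data at least twice a year. No dose, stopping or efficacy decision uses the tables in 13.4.5. This stands, and it confines the point to the reported rates. A reader might infer from 13.4.5 that toxicity in ineligible patients is discarded from the trial; the documents do not support that.

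Second, 13.7.1 already puts the inclusive population in the statistical chapter, so the plan does not settle on exclusion. This also stands. With no order of precedence, the tables could omit these patients; it cannot be said that they would.

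Third, the number is probably below 3. The allowance also covers cancellations, which 4.4 ties to receiving no therapy, and treatment violations in patients who may be fully eligible. Section 4.3.2 has sites verify eligibility before enrolment. Reaching 35 also requires the cohort added only after undue toxicity. All of this is fair, although the allowance is a planning figure and not a cap.

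Fourth, a reader might infer that excluded patients are more prone to events, so that the tables understate toxicity. The overlap of entry limits with listed risks makes that plausible for some events. Other criteria, such as marrow blasts of at least 10%, have no obvious link to toxicity, and the documents give neither the reasons for ineligibility nor any risk difference.

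**Conclusion.** The contradiction is real and unresolved. As written, 13.4.5 conflicts with the plan's own toxicity population in 11.1.1 and 13.7.1 and differs from the population counted in 13.6.1. The consequence is limited to the descriptive adverse-event rates and tables.

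The size rests on the assumption that 1 to 3 treated patients prove ineligible. That is at most about 9% to 10% of patients, but in a trial this small it can move a single rate by several points. A reader might take 12.5% against 20% as the expected error. It is only the extreme in which all three ineligible patients had the event; if none had it, the all-treated rate is 11.4%, slightly below the eligible-only rate. The documents do not establish the direction of any bias.

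**What to change.** In the first sentence of 13.4.5, replace the population (eligible patients who have started treatment) with: all patients who received at least one dose of MLN0128 (TAK-228), regardless of eligibility. This matches 11.1.1 and 13.7.1 and agrees with the treated-patient count in 13.6.1. If the team wants an eligible-only table, it can be added as a labelled supplement.

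The cost is one phrase. No new data are needed, because these events are already collected under 7.4.
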